## 8.2.2 Relationship to Study Intervention

The clinician's assessment of an AE's relationship to study intervention is part of the documentation process, but it is not a factor in determining what is or is not reported in the study. If there is any doubt as to whether a clinical observation is an AE, the event should be reported. All AEs must have their relationship to study intervention assessed. In a clinical trial, the study intervention must always be suspect. To help assess, the following guidelines are used.

- **Related** – The AE is known to occur with the study intervention, there is a reasonable possibility that the study intervention caused the AE, or there is a temporal relationship between the study intervention and event. Reasonable possibility means that there is evidence to suggest a causal relationship between the study intervention and the AE.
- **Not Related** – There is not a reasonable possibility that the administration of the study intervention caused the event, there is no temporal relationship between the study intervention and event onset, or an alternate etiology has been established.

## 8.2.3 Expectedness

[name] will be responsible for determining whether an AE is expected or unexpected. An AE will be considered unexpected if the nature, severity, or frequency of the event is not consistent with the risk information previously described for the study intervention.

## 8.3 Time Period and Frequency for Event Assessment and Follow-Up

The occurrence of an AE or SAE may come to the attention of study personnel during study visits and interviews of a study participant presenting for medical care, or upon review by a study monitor. All AEs including local and systemic reactions not meeting the criteria for SAEs will be captured on the appropriate RF. Information to be collected includes event description, time of onset, clinician's assessment of severity, relationship to study intervention (assessed only by those with the training and authority to make a diagnosis), and time of resolution/stabilization of the event. All AEs occurring while on study must be documented appropriately regardless of relationship. All AEs will be followed to adequate resolution.

Any medical condition that is present at the time that the participant is screened will be considered as baseline and not reported as an AE. However, if the study participant's condition deteriorates at any time during the study, it will be recorded as an AE. UPs will be recorded in the data collection system throughout the study.

Changes in the severity of an AE will be documented to allow an assessment of the duration of the event at each level of severity to be performed. AEs characterized as intermittent require documentation of onset and duration of each episode.

The PI will record all reportable events with start dates occurring any time after informed consent is obtained until 7 (for non-serious AEs) or 30 days (for SAEs) after the last day of study participation. At each study visit, the investigator will inquire about the occurrence of AE/SAEs since the last visit. Events will be followed for outcome information until resolution or stabilization.

All unresolved adverse events should be followed by the investigator until the events are resolved, the subject is lost to follow-up, or the adverse event is otherwise explained. At the last scheduled visit, the investigator should instruct each subject to report any subsequent event(s) that the subject, or the subject's personal physician, believes might reasonably be related to participation in this study. The investigator should notify the study sponsor of any death or adverse event occurring at any time after a subject has discontinued or terminated study participation that may reasonably be related to this study.

CONFIDENTIAL

## **8.4 Reporting Procedures – Notifying the IRB**

### **8.4.1 Adverse Event Reporting**

AE's will be reported to the NYU School of Medicine IRB based on institution guidelines found here: <https://med.nyu.edu/research/office-science-research/clinical-research/resources-researchers-study-teams/human-research-regulatory-affairs/nyu-school-medicine-institutional-review-boards#reportable-new-information>

### **8.4.2 Serious Adverse Event Reporting**

SAE's will be reported to the NYU School of Medicine IRB based on institution guidelines found here: <https://med.nyu.edu/research/office-science-research/clinical-research/resources-researchers-study-teams/human-research-regulatory-affairs/nyu-school-medicine-institutional-review-boards#reportable-new-information>

### **8.4.3 Unanticipated Problem Reporting**

Incidents or events that meet the OHRP criteria for UPs require the creation and completion of an UP report form. It is the site investigator's responsibility to report UPs to their IRB and to the DCC/study sponsor. The UP report will include the following information:

- Protocol identifying information: protocol title and number, PI's name, and the IRB project number;
- A detailed description of the event, incident, experience, or outcome;
- An explanation of the basis for determining that the event, incident, experience, or outcome represents an UP;
- A description of any changes to the protocol or other corrective actions that have been taken or are proposed in response to the UP.

To satisfy the requirement for prompt reporting, UPs will be reported using the following timeline:

Incidents or events that meet the OHRP criteria for UPs require the creation and completion of an UP report form. It is the site investigator's responsibility to report UPs to their IRB and to the DCC/study sponsor. The UP report will include the following information:

- Protocol identifying information: protocol title and number, PI's name, and the IRB project number;
- A detailed description of the event, incident, experience, or outcome;
- An explanation of the basis for determining that the event, incident, experience, or outcome represents an UP;
- A description of any changes to the protocol or other corrective actions that have been taken or are proposed in response to the UP.

To satisfy the requirement for prompt reporting, UPs will be reported using the following timeline:

- UPs that are SAEs will be reported to the IRB and to the DCC/study sponsor within 5 days of the investigator becoming aware of the event.
- Any other UP will be reported to the IRB and to the DCC/study sponsor within 5 days of the investigator becoming aware of the problem.

CONFIDENTIAL

This material is the property of the NYU School of Medicine and NYU Langone Health. Do not disclose or use except as authorized in writing by the study sponsor Behavioral Intervention Template Version: 11 January 2019

All UPs should be reported to appropriate institutional officials (as required by an institution's written reporting procedures), the supporting agency head (or designee), and OHRP within 5 days of the IR's receipt of the report of the problem from the investigator.

#### **8.4.4 Reporting of Pregnancy**

Not applicable

### **8.5 Reporting Procedures – Notifying the Study Sponsor**

The study clinician will complete a SAE Form within the following timelines:

- All deaths and immediately life-threatening events, whether related or unrelated, will be recorded on the SAE Form and submitted to the DCC/study sponsor within 24 hours of site awareness. See Section 1, Key Roles for contact information.
- Other SAEs regardless of relationship will be submitted to the DCC/study sponsor within 72 hours of site awareness.

All SAEs will be followed until satisfactory resolution or until the site investigator deems the event to be chronic or the adherence to be stable. Other supporting documentation of the event may be requested by the DCC/study sponsor and should be provided as soon as possible.

As a follow-up to the initial report, within the following 48 hours of awareness of the event, the investigator shall provide further information, as applicable, on the unanticipated event or the unanticipated problem in the form of a written narrative. This should include a copy of the completed Unanticipated Problem form, and any other diagnostic information that will assist the understanding of the event. Significant new information on ongoing unanticipated adverse effects shall be provided promptly to the study sponsor.

### **8.6 Reporting Procedures – Participating Investigators**

Any adverse events will be appropriately communicated by the study team to study leadership at each of the participating institutions.

### **8.7 Study Halting Rules**

Administration of study agent will be halted when three grade 3 AEs determined to be "probably related" are reported to the DCC. The DCC will notify the study sponsor and investigators immediately when the third grade 3 event is reported and enrollment screens will stop accepting new study participants.

### **8.8 Safety Oversight**

It is the responsibility of the Principal Investigator to oversee the safety of the study at his/her site. This safety monitoring will include careful assessment and appropriate reporting of adverse events as noted above, as well as the construction and implementation of a site data and safety-monitoring plan. Medical monitoring will include a regular assessment of the number and type of serious adverse events.

Data Safety Monitoring (Security Risk Questionnaire can be found in the appendices)

Data Safety Monitoring Plan: Data management and security Each site will be responsible for maintaining their data and maintaining security. As a team, we intend to use standard IRB-approved and HIPAA-compliant measures to maintain confidentiality, privacy and data security. Data privacy and security procedures will include: a) training staff on data sensitivity and protocols for safeguarding confidentiality; b) storing and processing sensitive hardcopy in a secured, centralized location; c) securing sensitive hardcopy in locked files when not in use; d) removing names, addresses, and other direct identifiers from

CONFIDENTIAL

This material is the property of the NYU School of Medicine and NYU Langone Health. Do not disclose or use except as authorized in writing by the study sponsor Behavioral Intervention Template Version: 11 January 2019

hardcopy and computer-readable data when they are no longer necessary for patient tracking and then using encrypted codes for subsequent identification of participants; e) destroying all identifiable linkages to data after data accuracy has been verified and final analyses have been completed; f) using restricted logon identification and password protection computer protocols for all computerized entry, retrieval, and analysis. Participant safety and plan for detecting issues and minimizing participant risk during study Participants will be at minimal risk and have the right to withdraw from the study at any time. All identifiable information will be maintained by the investigators. The principal investigators and project managers at all sites will be responsible for monitoring the scientific integrity and participant safety for the full duration of the study. They will meet weekly to discuss the progress of the study. The proposed study will use survey instruments and EHR tools that are similar to those developed by the investigators in a previous study. We do not anticipate any significant physical, psychological, or social risk to the study patients. All risks and benefits of participation will be explained to participants and included in the written informed consent forms. The only adverse event that can be experienced in this study is a break in confidentiality of study participants. Any adverse events will be reported to the IRB as required.

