#### 4.2.3 Exploratory Endpoints

## 5 Study Enrollment and Withdrawal

### 5.1 Inclusion Criteria

In order to be eligible to participate in this study, an individual must meet all of the following criteria:

Provider Inclusion Criteria: (a) Fulltime primary care provider (MD/DO, NP) practicing at the participating FHCs or FGPs and, (b) Provide care to at least five patients with a diagnosis of pre-diabetes.

Patient Inclusion Criteria:

In order to be eligible to participate in this study, an individual must meet all of the following criteria:

1. 18 years or older,  $BMI \geq 25 \text{ kg/m}^2$  ( $> 22 \text{ kg/m}^2$  if self-identified as Asian)
2. A diagnosis of prediabetes (either diagnosis of prediabetes or an HbA1C level of 5.7%-6.4% in past 18 months)
3. Baseline self-test a1c value of 5.4 to 6.4
4. Safe to engage in moderate physical exercise (as determined by their PCP)

CONFIDENTIAL

This material is the property of the NYU School of Medicine and NYU Langone Health. Do not disclose or use except as authorized in writing by the study sponsor Behavioral Intervention Template Version: 11 January 2019

5. Sufficient English to be able to complete the enrollment process
6. Has app capable device with data to use the dDPP application and receive text messages
7. NYU Langone Health Patient with assigned PCP on EPIC/EHR

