### **8.1.1 Definition of Adverse Events (AE)**

An **adverse event** (AE) is any symptom, sign, illness or experience that develops or worsens in severity during the course of the study. Intercurrent illnesses or injuries should be regarded as adverse events. Abnormal results of diagnostic procedures are considered to be adverse events if the abnormality:

- results in study withdrawal
- is associated with a serious adverse event
- is associated with clinical signs or symptoms

CONFIDENTIAL

This material is the property of the NYU School of Medicine and NYU Langone Health. Do not disclose or use except as authorized in writing by the study sponsor Behavioral Intervention Template Version: 11 January 2019

- leads to additional treatment or to further diagnostic tests
- is considered by the investigator to be of clinical significance

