#### **10.4.4 Safety Analyses**

We will periodically review participant records and report hospitalizations and deaths.

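### The 8.8 statement that a confidentiality break is the only possible adverse event contradicts 8.1.1, 8.3 and 8.7, and 10.4.4 plans no by-arm tabulation of adverse events beyond hospitalizations and deaths

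*Combined protocol and SAP*

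**What the plan says.** The protocol deals with adverse events in several places.

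- **8.1.1** defines an AE as "any symptom, sign, illness or experience that develops or worsens in severity during the course of the study" and adds: "Intercurrent illnesses or injuries should be regarded as adverse events".
- **8.1.2** lists six criteria that make an AE serious: death, threat to life, new or prolonged hospital stay, lasting or significant disability, congenital anomaly, and important medical event.
- **8.3** states: "All AEs occurring while on study must be documented appropriately regardless of relationship". It requires the investigator to ask about AEs and serious AEs (SAEs) at each study visit. Conditions already present at screening are excluded unless they deteriorate.
- **8.7** sets a halting rule that counts grade 3 AEs judged probably related.
- **8.8** requires AEs to be assessed and reported and the number and type of SAEs to be assessed regularly. Its data safety monitoring plan then says: "The only adverse event that can be experienced in this study is a break in confidentiality of study participants". The next sentence is: "Any adverse events will be reported to the IRB as required".
- **14.1** has AE data entered in REDCap.
- **10.4.4**, the whole of the safety analysis, reads: "We will periodically review participant records and report hospitalizations and deaths".

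**The concern.** There are two separate problems.

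The first is a contradiction. If a confidentiality break is the only AE that can occur, then 8.1.1 and 8.3 define and collect events that 8.8 calls impossible, and the 8.7 halting rule counts clinical events that 8.8 says cannot arise.

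The second is a gap between collection and analysis, which remains however the 8.8 sentence is read. Section 8 has staff collect a broad set of events, while 10.4.4 commits to reporting a narrow part of it and mentions no arm, denominator or time window. Followed as written, the plan would leave most of the collected safety data without a stated output.

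This matters because of what the trial tests. The primary hypothesis in 10.2 includes a greater increase in physical activity with the tool suite, and 10.6.1 states that neither patients nor providers are blinded. A trial that expects more activity in its intervention arms should be able to say whether injuries, or privacy breaches, differed between arms.

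**Working it through.** No arithmetic on rates is possible, because the documents give no expected AE frequency and no safety sample size. The check sets the sections side by side.

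**Step 1: is the 8.8 sentence compatible with the rest of section 8?**

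| Section | What it treats as a possible AE |
|---|---|
| 8.1.1 | Any new or worsening symptom, sign, illness or experience, including intercurrent illness and injury |
| 8.3 | The same set, documented regardless of relationship to the intervention |
| 8.7 | Events severe enough to be graded 3, with a probable relationship |
| 8.8 | A confidentiality break and nothing else |

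A sprained ankle during follow-up is an AE under 8.1.1, must be documented under 8.3, and cannot exist under a literal reading of 8.8. The contradiction is real. It is limited to new or worsening conditions, because 8.3 sets aside stable conditions present at screening.

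**Step 2: which collected events does 10.4.4 cover?**

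| Event type | Collected or reported under | Named in 10.4.4 |
|---|---|---|
| Death | 8.1.2, 8.3 | Yes |
| New or prolonged hospital stay | 8.1.2, 8.3 | Yes |
| Life-threatening event | 8.1.2, 8.3 | No |
| Disability or incapacity | 8.1.2, 8.3 | No |
| Congenital anomaly | 8.1.2, 8.3 | No |
| Important medical event | 8.1.2, 8.3 | No |
| Non-serious AE | 8.1.1, 8.3 | No |
| Confidentiality breach | 8.8; 8.4.3 if it meets the unanticipated-problem criteria | No |

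Of the six SAE criteria, two are named, which leaves 6 − 2 = 4 without a planned tabulation unless the same event also leads to hospitalization or death. Non-serious AEs have the same gap. So does the one event that 8.8 names.

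**Step 3: is a comparison by arm planned elsewhere?** The regular assessment of SAEs in 8.8 does not mention arms. Section 10.4.1 promises a summary by treatment group for the primary and other variables but does not name AEs. No section states a comparison of AEs by arm.

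**Step 4: are the data already required?** Yes. Section 8.3 requires collection at each visit, and 14.1 puts AEs in REDCap.

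**Step 5: is collection at risk?** The patient visit lists in 7.3.2, 7.3.3.2 and 7.3.4 (baseline, week 1 to 2, and months 1, 3, 6, 12 and 18) cover consent, onboarding, questionnaires and experience interviews. None lists AE inquiry, although 8.3 requires it at each visit. That is a reason for concern about completeness, but it does not show that events will be missed.

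**The case against.** The strongest defence is that the 8.8 sentence is a risk forecast and not a recording rule. It follows a statement that no significant physical, psychological or social risk is anticipated. The next sentence sends any AEs to the IRB, and earlier text in 8.8 refers back to the preceding sections for assessment and reporting. On that reading there is one collection rule, in 8.1.1 and 8.3, and one badly worded forecast. This is a fair account of what was probably intended. It means 8.8 does not by itself set recorded clinical AEs to zero. It does not remove the contradiction, since the sentence speaks of what can be experienced and not of what is expected or related. It also leaves the gap in 10.4.4 untouched.

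Other parts of the defence also hold. Section 8.8 does require regular review of SAEs, so the categories missing from 10.4.4 are monitored. A confidentiality breach that meets the unanticipated-problem criteria must be reported within 5 days under 8.4.3. An injury that leads to hospitalization would appear under 10.4.4. But these are oversight and reporting routes, and none is an analysis by randomized arm.

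A reader might infer three stronger conclusions that the documents do not support:

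- **Harms will be under-recorded.** Section 8.3 requires inquiry at every visit and documentation regardless of relationship. The omission from the visit lists makes under-recording possible, not established.
- **The 8.8 sentence contradicts the eligibility rules on exercise.** Requiring that the primary care provider judge exercise safe, and excluding patients who cannot exercise moderately, are risk-reducing steps. They are compatible with a low-risk forecast.
- **A comparison by arm would measure the harms of diet and exercise.** Under 4.1 every arm receives the app. The comparison would show harms of the added messaging and provider tools, which is the randomized question.

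**Conclusion.** The point holds in two parts. The 8.8 sentence contradicts 8.1.1, 8.3 and 8.7, and these must be reconciled. Independently of that, 10.4.4 leaves non-serious AEs, four of the six SAE criteria (where no hospitalization or death is involved) and confidentiality breaches with no planned tabulation, and no comparison by arm is planned for any safety event.

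The size cannot be expressed as a number of patients, because the documents give no AE rate. The conclusion assumes only that 10.4.4 is followed as written and that no safety tabulation is specified in a document outside the protocol and SAP. The primary estimate, its power and its error rate are not affected. What is affected is the trial's ability to report harms by arm from data it already undertakes to collect.

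**What to change.** 1. **Section 8.8.** Replace the sentence with a cross-reference, for example: *Adverse events are as defined in 8.1.1 and collected as described in 8.3.* If the intention was that a confidentiality break is the only anticipated study-related risk, say that as a forecast, in words that cannot be read as a definition. Check that 8.7 is consistent with the result; what the halting rule should be is for the investigators to settle.
2. **Section 10.4.4.** Replace with, for example: *All AEs and SAEs collected under 8.3, including confidentiality breaches, hospitalizations and deaths, will be tabulated by randomized arm, giving the number of patients with at least one event, the number of events, and the denominator.* Follow-up time per arm is worth adding, because 5.7.2 ends data collection at withdrawal.
3. **Sections 7.3.2 to 7.3.4.** Bring the visit lists into line with 8.3 by listing AE inquiry.

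The cost is a few sentences and one extra table, built from data that 8.3 and 14.1 already require. No new data collection is needed beyond what 8.3 already asks for.

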## 9 Clinical Monitoring

Clinical site monitoring is conducted to ensure that the rights and well-being of human subjects are protected, that the reported trial data are accurate, complete, and verifiable, and that the conduct of the trial is in compliance with the currently approved protocol/amendment(s), with GCP, and with applicable regulatory requirement(s).

- Monitoring for this study will be performed by [name] and [name].
- Centralized monitoring will be performed throughout the study to ensure comprehensive data verification of endpoints, safety, and the distribution of monitoring reports
- Study staff will perform internal quality management of study conduct, data collection, documentation and completion.

